3.2. Secondary Endpoints

3.2.1. Key Secondary Endpoint: Factor VIII Activity > 5% at 15 Months Postinfusion

Samples to assess circulating factor VIII activity levels will be analyzed by central and local laboratories.

- In the central laboratory, FVIII activity will be assessed both by chromogenic and one-stage clotting assay.
- In local laboratories, FVIII activity will be assessed by chromogenic or one-stage clotting assay based on standard practice.

Primary and secondary objectives are based on the chromogenic assay results from the central laboratory. Central chromogenic assay results will be used as the primary FVIII activity measurement as this approach is considered the most conservative because it resulted in the lowest activity levels in the Phase 1b/2 study (C3731001).

In 2022, FVIII activity assays were validated to an extended upper limit of quantification (ULoQ) and to neutralize the effect of direct oral anticoagulant (DOAC) for participants treated by DOAC. These further validated assays have been implemented by the central laboratory since 15 June 2022. As such, the back-up of samples assessed before this date and corresponding to these criteria (i.e., the initial result was above the ULoQ or the participant was on DOAC at the time of sample collection) have been retested. As a result, when applicable, the initial FVIII activity levels will be replaced by the appropriate retested levels and the later will be included in the summary/analysis.

Following the implementation of further validated assays, only the following FVIII activity levels listed below will be considered as appropriate and included in the statistical analysis and summary.

- FVIII activity results with DOAC reversal agent if the participant was on DOAC at the time of sample collection.
- FVIII activity results without DOAC reversal agent if the participant was not on DOAC at the time of sample collection.

In addition, the initial FVIII activity results collected prior to the further assay validation that did not require retesting will also be considered as ‘appropriate’ and included in the analysis and summary.

For completeness, all FVIII activity results (from initial and retested samples) will be included in data listings.

Any sample taken within 72 hours for standard half-life products or 120 hours for extended half-life products after administering exogenous FVIII replacement therapy for any purpose (including treatment of bleeding or prevention purposes) will be excluded. When multiple appropriate FVIII activity observations are collected on the same day for a participant, the average level of these observations will be used for the given day. Additionally, any FVIII activity levels after the resumption of FVIII prophylaxis regimen (if necessary) will be replaced with 0.9% for analysis purposes, and therefore considered as having FVIII activity \leq 5%. FVIII activity collected at unscheduled visits will be mapped to a visit if the data collection date falls into the protocol-defined visit window.

Participants who prematurely discontinue from the study prior to reaching Month 15 visit will be considered as having FVIII activity \leq 5% for the main analysis of this endpoint.

The FVIII activity level at 15 months post PF-07055480 infusion will include all appropriate FVIII activity data collected around the Week 65 visit (from Week 63 through Week 67), including unscheduled visit observations. In a case when multiple observations fall into the same visit window, an average FVIII activity level will be taken over these observations and included in the analysis.

For participants who have not discontinued from the study before Week 65 visit and have not resumed prophylaxis, if there are no appropriate FVIII activity levels for a participant in the main analysis population during the visit window of Week 65 visit (from Week 63 through

Week 67), the missing FVIII activity level will be imputed with the earliest appropriate FVIII activity level collected post Week 65 visit window. In case there are no appropriate FVIII activity levels post Week 65 visit window, the FVIII activity at Week 65 will be considered as missing and excluded from the assessment.

3.2.2. Key Secondary Endpoint: Treated ABR

Treated ABR from Week 12 [Day 78] through at least 15 months (up to data cutoff) following PF-07055480 infusion is considered as another key secondary endpoint. The data collection and endpoint derivation are similar to those described for Total ABR in [Section 3.1.1](#). In addition, Treated ABR will be reported by yearly interval as well as by cumulative follow-up interval after PF-07055480 infusion as secondary endpoints.

3.2.3. Annualized Infusion Rate (AIR) of Exogenous FVIII

AIR of exogenous FVIII replacement following PF-07055480 infusion from Week 12 [Day 78] through at least 15 months (up to data cutoff) after PF-07055480 infusion is considered as a secondary endpoint and will be compared with AIR during prior FVIII prophylaxis replacement regimen.

All infusions during the observation time period for any purpose (to treat bleeding, for preventive purpose, perioperative, or if FVIII prophylaxis regimen is resumed) will be included in the calculation of AIR. AIR data after PF-07055480 infusion will additionally be analyzed for the yearly intervals as well as cumulative follow-up intervals as separate secondary endpoints.

For participants with incomplete data for the entire yearly time period, including participants who discontinued prior to completing the study, all data during that period will be annualized and summarized utilizing the number of days of follow-up during the given time period. AIR for each participant will be calculated as below:

$$\text{AIR} = \frac{(\text{Number of infusions for any purpose during the given time period}) \times 365.25}{(\text{Number of days of follow-up in the given time period})}$$

Same as explained in [Section 3.1.1](#), the follow-up period will exclude the first 11 weeks (77 days). The denominator in the above calculation for postinfusion up to data cutoff, Month 15 interval and cumulative follow-up intervals will be [the last date in the given time period – (Date of PF-07055480 infusion) – 77 days +1]. If the participant discontinues from study before the end of the prespecified time period, the last date in the given time period will be the date of study discontinuation.

If a participant has to resume FVIII prophylaxis treatment, prophylaxis FVIII infusion data will not have to be reported on the eDiary (or conveyed to the study site staff on a contemporaneous basis) after Week 78 (Month 18). The eDiary will continue to collect bleeds and non-prophylactic infusions (e.g., on-demand and preventative) throughout the course of the study. The prophylaxis infusion data will be derived from the prescribed FVIII product information and included in the AIR calculation.

The AIR data collected in the lead-in study (C0371004) while participants were on the FVIII prophylaxis replacement regimen up to the time period prior to PF-07055480 infusion in this study will be annualized using the same formula presented above and used for comparison. During this study, all infusions from Week 12 [Day 78] will be included in the AIR calculation including those to treat bleeding (on-demand), for prophylaxis, for preventive purposes, or perioperative infusions.

3.2.4. FVIII Activity Level from Week 12 through 15 Months Postinfusion

The beginning of steady state will be considered as Week 12 for analysis purposes within this Phase 3 study. Additionally, the data from this Phase 3 study will be utilized to confirm the timing of the onset of steady state.

The Factor VIII activity from Week 12 through 15 months postinfusion will be calculated for each participant as a geometric mean of all appropriate FVIII activity measures (including unscheduled visit observations) from Week 12 through 15 months (up to the upper bound of the Month 15 visit window: Week 67) after PF-07055480 infusion based on central chromogenic assay and one-state clotting assay separately. When multiple appropriate FVIII activity observations are collected on the same day for a participant, the average level of these observations will be used for that given day. FVIII activity will be imputed with 0.9% after the participants have resumed prophylaxis regimen up to data cutoff or Week 67, whichever occurs earlier.

If a participant has missing data for a study visit or has otherwise discontinued due to any reasons other than lack of efficacy but has not resumed prophylaxis prior to completing the designated follow-up period, all available data will be included to calculate geometric mean despite the missed measurements. Specifically, imputation of FVIII activity will be applied per scenarios listed below:

- Resumed prophylaxis but remained in the study: Impute FVIII activity with 0.9% at any protocol-defined visits post resumption of prophylaxis until data cutoff or Week 67, whichever occurs earlier.
- Resumed prophylaxis and then discontinued from the study due to any reasons: Impute FVIII activity with 0.9% at any protocol-defined visits post resumption of prophylaxis until data cutoff or Week 67, whichever occurs earlier.
- Discontinued from study due to lack of efficacy but has not resumed prophylaxis: Impute FVIII activity with 0.9% at any protocol-defined visits post study discontinuation until data cutoff or Week 67, whichever occurs earlier.
- Discontinued from the study due to any reasons other than lack of efficacy but has not resumed prophylaxis: No imputation will be applied. FVIII activity after study discontinuation will be considered missing.

3.2.5. FVIII Activity Level by Visit

Mapping for unscheduled visit observations and exclusion in FVIII activity data are described in [Section 3.2.1](#). FVIII activity analyzed by the central laboratory will be reported for chromogenic assay and one-state clotting assay separately. FVIII activity will be imputed with 0.9% through data cutoff after the participants have resumed prophylaxis regimen and after they discontinued from the study due to lack of efficacy. FVIII activity won't be imputed after participants discontinue from the study due to reasons other than lack of efficacy if they have not resumed prophylaxis. Specifically, imputation of FVIII activity will be applied per scenarios listed below:

- Resumed prophylaxis but remained in the study: Impute FVIII activity with 0.9% at any protocol-defined visits post resumption of prophylaxis until data cutoff.
- Resumed prophylaxis and then discontinued from the study due to any reasons: Impute FVIII activity with 0.9% at any protocol-defined visits post resumption of prophylaxis until data cutoff.
- Discontinued from study due to lack of efficacy but has not resumed prophylaxis: Impute FVIII activity with 0.9% at any protocol-defined visits post study discontinuation until data cutoff.
- Discontinued from the study due to any reasons other than lack of efficacy but has not resumed prophylaxis: No imputation will be applied. FVIII activity after study discontinuation will be considered missing.

FVIII activity levels by visit will be summarized. In addition, the percentage of participants with FVIII activity level $\geq 40\%$ will be reported by visit up to data cutoff.

3.2.6. Annualized FVIII Consumption

Annualized FVIII consumption will be reported by international unit (IU)/kg and total units (in IU), and a similar approach of data collection and endpoint derivation as described in [Section 3.2.3](#) above for AIR will be used. FVIII consumption during the first 11 weeks will not be included.

3.2.7. Annualized Bleeding Rate of Specific Type

The ABR of specific type from Week 12 [Day 78] through at least 15 months (up to data cutoff) following PF-07055480 infusion as well as by yearly interval and by cumulative follow-up interval after the first 15 months will be reported separately by:

- Cause (spontaneous or traumatic)
- Location type (in all joints, in target joints, or in soft tissue)

Soft tissue includes soft tissue, muscle, and other (i.e., soft tissue/muscle/other). Per Protocol Appendix 7, a target joint is defined as a major joint (e.g., hip, elbow, wrist, shoulder, knee, and ankle) into which repeated bleeds occur (3 or more spontaneous bleeds into a single joint within a consecutive 6-month period). A target joint is considered resolved when there are

≤ 2 bleeds into the joint within a 12-month period. The investigator will assess the health of the target joint(s), identified at screening, as specified in the schedule of activities (SoA) of the protocol. Once a target joint is identified for a participant, the bleedings on this target joint will always be included in the ABR by target joint calculation even if the target joint is considered to have been resolved for any time period. The data collection and endpoint derivation are similar to what's described for Total ABR in [Section 3.1.1](#).

3.2.8. Total ABR by Cause and by Location

Total ABR (treated and untreated) by cause and by location from Week 12 [Day 78] through at least 15 months (up to data cutoff) following PF-07055480 infusion is considered as a secondary endpoint. Total ABR by location will be also reported by yearly interval as well as by cumulative follow-up interval post PF-07055480 infusion. The data collection and endpoint derivation are similar to those described for Total ABR in [Section 3.1.1](#) above.

3.2.9. Percentage of Participants without Bleeds

The percentage of participants without treated bleeds and the percentage of participants without treated and untreated bleeds will be reported for the observation period from Day 78 through data cutoff post PF-07055480 infusion, and by yearly interval (defined in [Section 3.1.1](#)) as well as by cumulative follow-up interval post PF-07055480 infusion as secondary endpoints. Data after resumption of prophylaxis or study discontinuation will be excluded from the summary. The percentage of participants without bleeds at baseline will be obtained from the lead-in study up to preinfusion of PF-07055480 and will also be reported for comparison.

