3. OBJECTIVES, ESTIMANDS, AND ENDPOINTS

Objectives	Endpoints
Primary Efficacy Objective	Primary Endpoint and Key Secondary Endpoints Primary Endpoint:

Evaluate the efficacy of a single infusion of PF-07055480 in participants ≥ 18 and <65 years of age with moderately severe to severe hemophilia A (FVIII C $\leq 1\%$).	
Total ABR (spontaneous and traumatic bleedings, treated and untreated) from Week 12 through at least 15 months following PF-07055480 infusion versus Total ABR on prior FVIII prophylaxis replacement regimen.

Objectives	Endpoints
	
Key Secondary Endpoints:
 
• FVIII activity level >5% at 15 months following infusion of PF-07055480.• ABR (spontaneous and traumatic treated bleedings) from Week 12 through at least 15 months following PF-07055480 infusion versus ABR on prior FVIII prophylaxis replacement regimen.
Secondary Efficacy Objectives	Secondary Efficacy Endpoints

• To demonstrate that the use of exogenous FVIII is significantly reduced post PF-07055480 infusion.• To assess additional efficacy parameters post PF-07055480 infusion including FVIII activity level, use of exogenous FVIII, information on bleeding events and PROs.	
Secondary Efficacy Endpoints
 
• AIR of exogenous FVIII from Week 12 through at least 15 months following infusion of PF-07055480 versus AIR on prior FVIII prophylaxis replacement regimen.• FVIII activity level from Week 12 through 15 months following infusion of PF-07055480. 
The following secondary parameters will be assessed from Week 12 through at least 15 months after PF-07055480 infusion and compared with prior FVIII prophylaxis replacement regimen:
 
• Annualized FVIII consumption.• ABR of specific type:
◦ by cause (spontaneous or traumatic)◦ by location (in joints, in target joints, or in soft tissue).• Total ABR by cause and by location.• Percentage of participants without bleeds. 
The following secondary parameters will be assessed by visit after PF-07055480 infusion:
 
• FVIII activity level• Change from baseline in joint health as measured by the HJHS instrument.

Objectives	Endpoints
	
• Change from baseline in the following PRO endpoints:
• Haem-A-QoL• HAL.

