
• Estimate the durability of efficacy up to 5 years after PF-07055480 infusion.	
The following parameters will be analyzed yearly or by visit as appropriate:
 
• ABR.• FVIII activity level.• AIR of exogenous FVIII.• Annualized FVIII consumption.• ABR of specific type:
○ by cause (spontaneous or traumatic).○ by location (in joint, in target joints, or in soft tissue).• Total ABR.• Total ABR by cause and by location.• Percentage of participants without bleeds.• Change from baseline in joint health as measured by the HJHS instrument.• Change from baseline in PRO endpoints: Haem-A-QoL and HAL. 
In addition, ABR, Total ABR, and AIR will be analyzed throughout the 5-year study period.

Secondary Safety Objective	Secondary Safety Endpoints

• To estimate the safety and tolerability of PF-07055480, including immunogenicity, for the study duration of 5 years after PF-07055480 infusion.	
• Incidence and severity of AEs.• Events of special interest (such as hypersensitivity reactions, clinically

Objectives	Endpoints
	
reported thrombotic events, and malignancy).
 
 • Immunogenicity: 
 ○ Antibodies against AAV6 capsid protein (nAbs and ADAs). ○ T-cell responses against AAV6 capsid and against the transgene. ○ FVIII inhibitors.
Tertiary/Exploratory	

 • To evaluate vector shedding and infectivity in body fluids. 	
 • Vector shedding and infectivity of PF-07055480 in plasma, saliva, PBMC, urine, and semen until negative on 3 consecutive occasions for each specimen type.

 • To evaluate exploratory pharmacodynamic biomarkers. 	
 • FVIII antigen levels. • Von Willebrand factor.

 • To compare joint health post PF-07055480 infusion to baseline and evaluate long-term joint outcomes. 	
 • Number of target joints. • Joint status as assessed by X-ray. • Joint status as assessed by ultrasound.

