Only new bleeds will be counted toward the number of bleeds for ABR calculation. New bleeds that occurred on the same date will be counted using the following algorithm to derive overall bleeds and bleeds by location type as displayed in [Table 7](#) below.

Table 7. Counting New Bleeds Occurring on the Same Date Based on Bleeding Time, Location Type, And Bleeding Site

Multiple new bleeding episodes occurring (regardless spontaneous or traumatic) on the same date	Same location type	Same bleeding site*	Counting toward overall bleeds	Counting toward bleeds by location type
Same date/time	Yes	No	One bleeding episode	One bleeding episode at the given location type
Same date/time	No	No	One bleeding episode	One bleeding episode for each location type
Same date but different time	Yes	No	Separate bleeding episodes	Separate bleeding episodes at the given location type
Same date but different time	No	No	Separate bleeding episodes	One bleeding episode for each location type

Note: Location type refers to joint and soft tissue/muscle/other. Bleeding site refers to the body location (e.g., left/right shoulder, left/right knee, left/right arm, etc.).

*Per the definition of new bleeds, there won't be multiple new bleeds occurring at the same bleeding sites on the same date.

The number of treated and untreated bleeding episodes from Week 12 [Day 78] through data cutoff (at least 15 months) after PF-07055480 infusion will contribute to the postinfusion Total ABR calculation of each participant, which is considered the primary endpoint. Total ABR during additional time periods postinfusion (as indicated below) will be analyzed as secondary endpoints. The following yearly intervals as well as cumulative follow-up intervals will be used for reporting Total ABR data postinfusion. Note: here and throughout, Year 2 summaries include data following Month 15 (Day 455) through Month 24 (Day 730).

Yearly Interval	Interval Derivation
Month 15	Day 77 < Month 15 ≤ Day 455
Year 2	Day 455 < Year 2 ≤ Day 730
Year 3	Day 730 < Year 3 ≤ Day 1095
Year 4	Day 1095 < Year 4 ≤ Day 1460
Year 5	Day 1460 < Year 5

Note: Day 1 is the day when PF-07055480 infusion started.

Cumulative follow-up interval	Interval Derivation
Cumulative follow up through 2 years postinfusion	Day 78 to Day 730
Cumulative follow up through 3 years postinfusion	Day 78 to Day 1095
Cumulative follow up through 4 years postinfusion	Day 78 to Day 1460

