Cumulative follow up through 5 years postinfusion	Day 78 to End of the study

For participants with incomplete data for the entire yearly time period, including participants who discontinued, all data during the specified period will be annualized and summarized utilizing the number of days of follow-up during the given time period (i.e., observation period). Total ABR for each participant will be calculated as below:

Total ABR =

$$\frac{(\text{Number of treated and untreated bleeding episodes during the given time period}) \times 365.25}{(\text{Number of days of follow-up in the given time period})}$$

Data before Week 12 postinfusion are excluded to account for the potential differences in participants' pharmacokinetics postinfusion. As a result, the denominator in the above calculation for the Month 15 and cumulative follow-up intervals will be [the last date in the given time period – (Date of PF-07055480 infusion) – 77 days +1].

For the primary endpoint assessment of Total ABR from Week 12 through at least 15 months (up to data cutoff), the number of bleeds post resumption of prophylaxis regimen or study discontinuation will be excluded. As a result, the denominator (i.e., number of days in the observation period) in the above Total ABR calculation will include days up to data cutoff, the day before resumption of prophylaxis regimen, or discontinuation date, whichever occurs earliest.

Total ABR during yearly intervals and cumulative follow-up intervals are considered as secondary endpoints. If the participant discontinues from study before the end of the prespecified observation period, the last date in the given observation period will be the date of study discontinuation. In addition, if FVIII prophylaxis regimen is resumed for a participant as defined in Protocol Section 6.5.1 then data collected on and after the date of prophylaxis resumption entered in the eCRF by the investigator will be excluded from the calculation of Total ABR by interval, which means the bleeding events will be excluded and the corresponding time period will be deducted as well.

Total ABR prior to PF-07055480 will be calculated using all treated and untreated bleeds documented during the lead-in study (C0371004) up to preinfusion of PF-07055480 and the respective number of days of follow-up within the lead-in study and preinfusion period using the same formula presented above.

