6.2.9. Percentage of Participants without Bleeds

Percentage of participants without treated bleeds will be reported for the same time periods as for Total ABR: from Week 12 through at least 15 months (up to data cutoff) post PF-07055480 infusion, by yearly interval as well as by cumulative follow-up interval. The yearly intervals and cumulative follow-up intervals are defined in [Section 3.1.1](#).

The percentage of participants without treated and untreated bleeds will be reported for the same time periods as for Total ABR: from Week 12 through at least 15 months (up to data cutoff) post PF-07055480 infusion, by yearly interval as well as by cumulative follow-up interval.

The summary tables will be provided for the time periods mentioned above and will include the number of participants included in the specified time interval, frequencies, and the percentage of participants with or without bleeding. The ‘Efficacy’ population will be used for the summary.

In addition, the percentage of participants without treated and untreated bleeds from Week 12 through data cutoff post PF-07055480 infusion will be reported for the ‘Dosed’ population.

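### The percentage of participants without bleeds is set beside its prior-prophylaxis value over windows of unequal length, with no adjustment for observation time (minor)

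*SAP*

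**What the plan says.** Protocol section 3 places this endpoint in the list of secondary parameters assessed from Week 12 and "compared with prior FVIII prophylaxis replacement regimen". It appears again under the 5-year durability objective.

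SAP 3.2.9 defines two percentages: no treated bleeds, and no treated or untreated bleeds. Each is reported from Day 78 to data cutoff, by yearly interval and by cumulative interval. The prior-prophylaxis value "at baseline will be obtained from the lead-in study up to preinfusion of PF-07055480 and will also be reported for comparison".

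For windows that end early, the same section says: "Data after resumption of prophylaxis or study discontinuation will be excluded from the summary". SAP 6.2.9 uses the Total ABR time periods, and its table shows "the number of participants included in the specified time interval, frequencies, and the percentage of participants with or without bleeding". For Total ABR, SAP 3.1.1 ends the observation period explicitly: it "will include days up to data cutoff, the day before resumption of prophylaxis regimen, or discontinuation date, whichever occurs earliest". Appendix 2 adds that missing data are not imputed for the bleed-free percentages.

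The interval tables in SAP 3.1.1 run Month 15 from Day 78 to Day 455, Year 2 to Day 730 and Year 3 to Day 1095. The row "Cumulative follow up through 2 years postinfusion" covers Day 78 to Day 730. The Efficacy population (SAP 4) needs at least 6 months of lead-in, and either at least 15 months postinfusion or discontinuation.

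**The concern.** ABR is divided by days of follow-up, so unequal windows do not bias it. The share of participants with no bleed is not divided by anything, and it can only fall as a window lengthens. Putting a share from roughly a year or more beside one from a window that may be little over six months mixes treatment effect with observation time. The same applies along the yearly series, where a shorter Year 2 can look like improvement and a longer Year 3 like loss of effect.

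At stake is how a protocol-listed secondary endpoint is read. No hypothesis test depends on it.

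**Working it through.** The plan states no expected percentage for this endpoint, so there is no figure to reproduce. The check asks how far the percentage moves because of window length.

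**Inputs**
- Postinfusion windows (SAP 3.1.1): Day 78–455 is 455 − 78 + 1 = 378 days, or 378/365.25 = 1.035 years. Day 78–730 is 653 days, or 1.788 years. Year 2 is 730 − 455 = 275 days. Year 3 is 1095 − 730 = 365 days.
- Pre-infusion window: at least 6 months of lead-in (SAP 4), with a screening and baseline period of about 6 weeks (SAP 2.3). Actual lengths are not given. Assumed range: 0.5 years; 0.5 + 42/365.25 = 0.615 years; 0.75 years; 1 year.
- Rates (Protocol 9.2): all bleeds 5/year before and 2/year after; treated bleeds 1/year after.
- Negative binomial dispersion k is not given. Assumed k = 0 (Poisson), 1 and 2.

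**Formula.** The chance of no bleed in t years at rate r is exp(−rt) for k = 0 and (1 + k·r·t)^(−1/k) otherwise. Gaps are post minus pre in percentage points, rounded after subtraction.

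**Step 1: no change in bleeding (5/year throughout), 378 days post.** Example for k = 1 and 6 months pre: 1/(1 + 2.5) = 28.6% before, 1/(1 + 5.175) = 16.2% after, gap −12.4.

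| Pre-window | k=0 | k=1 | k=2 |
|---|---|---|---|
| 6 months | −7.6 | −12.4 | −11.1 |
| 6 months + 6 weeks | −4.1 | −8.3 | −7.7 |
| 9 months | −1.8 | −4.9 | −4.6 |
| 1 year | −0.1 | −0.5 | −0.5 |

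**Step 2: planning rates (5 to 2/year), all bleeds.** Example for k = 1 and 6 months pre: 1/(1 + 2.070) = 32.6% after, minus 28.6%, is +4.0. With 6 months on both sides it is 1/(1 + 1) = 50.0% minus 28.6%, or +21.4.

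| Pre-window | Post 378 days (k=0/1/2) | Post Day 78–730 (k=0/1/2) |
|---|---|---|
| 6 months | +4.4 / +4.0 / +3.3 | −5.4 / −6.7 / −5.8 |
| 6 months + 6 weeks | +8.0 / +8.0 / +6.7 | −1.8 / −2.7 / −2.4 |
| 9 months | +10.3 / +11.5 / +9.8 | +0.4 / +0.8 / +0.7 |
| 1 year | +11.9 / +15.9 / +14.0 | +2.1 / +5.2 / +4.9 |

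Equal 6-month windows give +28.6 / +21.4 / +16.9.

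**Step 3: yearly series at a constant 1 treated bleed/year.** No lead-in length enters here.

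| Interval | Days | k=0 | k=1 | k=2 |
|---|---|---|---|---|
| Month 15 | 378 | 35.5% | 49.1% | 57.1% |
| Year 2 | 275 | 47.1% | 57.0% | 63.2% |
| Year 3 | 365 | 36.8% | 50.0% | 57.7% |

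The percentage rises by about 6 to 12 points in Year 2 and falls back in Year 3, with no change in bleeding.

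**Step 4: windows that end early.** Read together, SAP 3.1.1, 3.2.9, 6.2.9 and Appendix 2 imply that a participant is judged on the days observed before resumption or discontinuation. They also imply that a participant with no days in an interval is not counted in it. No sentence says so for this endpoint. SAP 6.1.1.2 and Appendix 2 do exclude participants who stopped before a yearly interval began, but they write that rule for the ABR analyses.

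**The case against.** The strongest reply is that nothing inferential rests on this percentage. Protocol 9.4.1 and SAP 5 say that it will be summarised, it is absent from Table 8, and the comparative question is carried by Total and Treated ABR, which are exposure-adjusted. The interval lengths are disclosed, the fixed 378-day Month 15 interval is already reported, and Month 15 and Year 3 differ by only 13 days, about 1 point in Step 3. All of this stands, and it is why the point is minor. None of it makes the pre and post percentages comparable.

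A reader might go further and infer that the plan will make an effective treatment look worse than prophylaxis. The documents do not support that. In Step 2 the sign reverses only for Day 78–730 with a pre-window of 6 months or 6 months plus 6 weeks, and the reversal is gone at 9 months. A lead-in longer than the postinfusion window would push the other way.

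A reader might also infer that participants cut short have no counting rule at all. Step 4 shows that the rule is implied; a confirming sentence is what is missing. Two of the three resumption criteria in Protocol 6.5.1 are repeated spontaneous bleeds. A participant who resumes on bleeds inside the window is therefore already not bleed-free on the all-bleeds percentage. The listing in SAP 6.1.1.3 and the resumption summary in SAP 6.2.3.2 give further context.

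**Conclusion.** The concern holds as a minor one. Followed exactly, the plan reports pre and post percentages that are not exposure-matched, and a yearly series that moves with interval length. That these effects exist follows from the plan's own windows; their size does not.

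Against 378 days post, the shift at an unchanged 5 bleeds/year runs from roughly 8–12 points against gene therapy with a 6-month pre-window to essentially none at 1 year. These values rest on assumed dispersion and assumed lead-in lengths. The Year 2 rise in Step 3 depends on the assumed dispersion and on full observation of each interval.

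The primary and key secondary conclusions and the type I error are unaffected.

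**What to change.** In SAP 3.2.9 and 6.2.9:

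1. Keep the existing to-cutoff, yearly and cumulative percentages. Show observation time (median, range) beside each, and note that they are not exposure-matched.
2. For both percentages, add a pre/post table over equal 6-month windows: the latest 6 months before infusion, already used for Total ABR in SAP 6.1.1.2, against Day 78–260 and Day 273–455 (183 days each). The later window guards against missing a loss of effect.
3. State that a participant is judged on observed days up to the day before resumption or to discontinuation, and that one with no days in a window leaves the denominator, with the number left out shown.
4. Rule 3 removes earlier resumers, especially from Day 273–455. Beside the matched table, show a labelled sensitivity analysis that keeps anyone who resumed prophylaxis before or during the window in the denominator as not bleed-free.

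The cost is SAP wording, one table and one sensitivity analysis from data already collected. The protocol-listed comparison stays as it is. The drawbacks are that the matched windows use less follow-up, and that the sensitivity analysis handles resumption differently from the ABR estimand.
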